7.2 Second Vaccination (Day 57; +14 days)

The date for this visit will be calculated 56 days from the date of the first study vaccination. A maximum window period of +14 days will be allowed for this visit. Parents will be contacted by phone few days before the visit to remind them of the appointment. Participants who miss the scheduled visit date will be prompted to re-schedule for the missed visit. The following procedures will be carried out at this visit:

- 1. Study staff will confirm participant's identity.
- 2. Check for any adverse events since last visit and record them in the source note and eCRF if applicable. Update medical history including follow-up of prior AEs.
- 3. Collection and review of the diary cards if not already collected by field worker earlier.
- 4. Check for use/administration of any medication/vaccine since last visit. Any medication taken for the treatment of the illness or vaccine administered will also be recorded in the relevant section of the CRF.
- 5. Conduct physical examination and vital examination and record the information on the CRF. Results will be reviewed by study staff and discussed with the parent. Any AEs that have occurred will be recorded in the appropriate section(s) of the CRF.
- 6. Check for any contraindication to vaccination. Reschedule visit if the infant is experiencing an illness that is temporary contraindication to vaccination.
- 7. Vaccines will be administered by an unblinded study staff if participant does not meet any contraindication to Investigational Medicinal Product (IMP) administration. The participant will receive a dose of vaccine bearing the same randomization code as for visit 1. A section of study eCRF will be completed that records information about vaccines received, date and time.
- 8. Procedures 5-7 under section 7.1 above will be repeated.

9. Remind the parent of the safety follow up visit and phone call by the field officer and advise him/her on the next clinic visit after 28 days.

Safety Follow-Up

- 1. Participants parent/LAR will complete the Diary Card daily, reporting solicited reactions experienced and medications taken from the evening of D57 through D63 after vaccination.
- 2. Study staff will make a physical home visit on Days 58 (+1 day) and Day 64 (+2 day) and a telephone call to the participant's parent/LAR on Day 61 (+2) to determine the child's health status and to support completion of the PIDC. In case the child experiences any illness during this period, they will be referred to the study clinic for further evaluation and treatment.
- 3. Completed PIDC can be collected by the field officer at on Day 64 visit or the parent can bring it to the site at the next visit, if parents were not available during the home visit.
- 4. The parent/LAR will be instructed that if the participant later experiences an AE requiring medical care, the parent should inform the investigator as soon as possible and seek medical care as appropriate. If the participant visits a health care provider, the participant parent/LAR should be sure to inform the health care provider of participation in this study and give the health care provider the contact information for the investigator.
- 5. The data in the PIDC collected by the parents will be reviewed by the study physician/designee and entered in the CRF. Any solicited reaction extending beyond 7 days after vaccination will also be recorded on the PIDC/CRF with date of resolution (if available) and the highest severity during the occurrence. Also, unsolicited AEs will be captured up to 28 days after each vaccination and SAEs including suspicion of intussusception will be recorded at all times between first vaccination and last visit. These will be managed medically as needed.

7.3 Final Study Visit (Day 85; +14)

The date for this visit will be calculated 28 days from the date of last vaccination. A maximum window period of +14 days will be allowed for this visit. Parents will be contacted for the participants who miss the scheduled visit date. The following procedures will be conducted:

- 1. Study staff will confirm participant's identity.
- 2. Review / update address and contact details.
- 3. Check for any adverse events since last visit and record them in the source note and eCRF if applicable. Update medical history including follow-up of prior SAEs. Ensure all ongoing AEs are followed up as per the protocol.
- 4. Collection and review of the diary cards if not already collected by field worker earlier.
- 5. Check for use/administration of any medication/vaccine since last visit. Any medication taken for the treatment of the illness or vaccine administered will also be recorded in the relevant section of the CRF.
- 6. Perform physical examination.
- 7. Collect up to 2 mL of blood for immunological assay.
- 8. Review vaccination history and advise the parent/LAR on future vaccination of the infant.
- 9. Complete the study termination/completion form

7.4 Early Termination

Participant parents/LARs have the right to decline study treatment or procedures for any reason and at any time during the study. If a participant parent/LAR declines further vaccination or study procedures (but continues in the study for safety assessment) this will be recorded as a study deviation and the reason will be clearly documented in the source document. The participant parent/LAR will be encouraged to have their child complete the remaining applicable safetyrelated follow-ups. A blood sample will not be collected in infants who miss one of the vaccinations. If the participant parent/LAR does not wish to remain in the study by declining any follow-ups or procedures, the participant parent/LAR can choose to withdraw consent and be withdrawn from the study.

The participants may be withdrawn from the study for any of the following reasons:

- If parent/LAR of participant wishes to withdraw consent.
- If the Principal Investigator (PI) decides that withdrawal is in the best interest of the participant.
- Significant non-compliance with treatment regimen or trial requirements.
- Participant is lost to follow-up.
- The sponsor/manufacturer recommends to terminate the study.
- Governing IRBs recommends to terminate the study.

In all cases, where the participant is withdrawn from the study the reason for withdrawal will be documented in an appropriate section of the eCRF. However, the data collected up to the last contact will be part of the analysis. In the event of withdrawal from study, reasonable efforts should be made to conduct the following procedures:

- Review diary card if still in use prior to withdrawal.
- Updating any ongoing AE/SAEs that remain ongoing at time of participant's last visit prior to withdrawal.
- Query about AEs, SAEs and concomitant medications since the last visit.
- Conduct physical examination.
- Update contact information.

Strategies to maintain retention in the trial include treating them respectfully, making sure they understand the study and potential side effects, and close communication with each participant parent/LAR about how the study unfolds. Given the short duration of the trial and anticipated side effects of the study vaccines, participant withdrawal and loss of follow-up is expected to be low. To prevent delays in subject visits and lost to follow-up, the study team will ensure that valid contact details are obtained prior to enrollment so that the parents/LARs can be reminded by phone at least two day before their scheduled visit. In the event of a missed visit, the participant parent/LAR will be contacted by phone; if that fails, a home visit within 3 days of the scheduled visit will be made by the field worker. A participant who cannot be located after at least 3 documented contact efforts will be considered lost to follow-up. Efforts to contact will be classified as lost to follow-up. A participant who is not vaccinated within the window of Visit 2 may be continued in the study, vaccinated outside of the window at the discretion of the investigator, and followed up according to guidance in the protocol. These cases if any will be

considered as protocol deviations and will be notified to the IEC/IRB in the progress reports and also be included in the list of protocol deviations in the study report. Participants who discontinue after enrollment will not be replaced.

POLYVAC and PATH must be informed within 48 hours of all instances of the premature termination of a participant's participation in the trial.

If the participant develops a reaction to study vaccine which the investigator believes threatens the participant's well-being, the withdrawn participant must be treated or transferred to a treatment facility.

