Vaccinated participants will be observed for immediate adverse events for 30 minutes after each vaccination. Active surveillance for vaccine reactogenicity (solicited reactions) over the 7-day period after each vaccination, unsolicited AEs for 4 weeks after each vaccination and SAEs including intussusception over the period between first vaccination and four weeks after the last vaccination will be conducted for all infants.

This protocol will have extensive safety monitoring in place. At the performing site level, the study site investigators and their clinical staff will be responsible for continuous close safety monitoring of all study participants and for alerting the protocol team if unexpected concerns arise. An team of vaccine experts, Safety Review Committee (SRC) composed of a group of physicians which include but not limit to the designated investigator from study team and the Medical Officer(s) from POLYVAC and PATH, a Pharmacovigilance/Medical officer from the CRO and an independent vaccine expert will be closely following the study for safety oversight. The SRC may seek independent expert medical opinion as dictated by the occurrence of certain events.

The SRC will have provision of expedited meeting that could be triggered by reporting of predefined AEs. The SRC may also seek independent expert medical opinion as dictated by the occurrence of certain events.

Study Sites

The study will be conducted at one district each of Nam Dinh and Quang Ninh provinces in Vietnam.

1. Nam Dinh Province:

- The study activities will be conducted at approximately 12 Commune health centers in Vu Ban district.
- Data entry/CRF storage at the Nam Dinh Provincial Preventive Medicine Center (PPMC).
- 2. Quang Ninh Province:
 - The study activities will be conducted at approximately 12 Commune health centers in Quang Yen district.
 - A blood sample will be collected from all infants participating in this study at this site.
 - Data entry/CRF storage at the Quang Ninh CDC.

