5.1.3 Continued Eligibility Confirmation for subsequent vaccination

The following events constitute absolute contraindications to rotavirus vaccination and all participants should be evaluated for these before administration of second dose of the study vaccine. If any of these events occur during the study, the participant must not receive additional doses of the vaccine but should be appropriately followed up for safety by the Investigator.

- Hypersensitivity reaction following the administration of the study vaccine.
- Any uncorrected congenital malformation of the gastrointestinal tract (such as Meckel's diverticulum) which is diagnosed after the first vaccination and that would predispose for intussusception.
- Infants with any history of intussusception.
- Severe combined immunodeficiency (SCID).
- Detection of one or more of the exclusion criteria during dosing period.

The following events constitute contraindications to administration of the study vaccine at that point in time; if any of these events occur at the time scheduled for vaccination, the participant may be vaccinated at a later date or withdrawn at the discretion of the Investigator.

- Acute disease and / or fever at the time of vaccination.
 - Acute disease is defined as the presence of a moderate or severe illness with or without fever. All vaccines can be administered to persons with a minor illness such as mild upper respiratory infection without fever.
 - Fever is defined as temperature $\geq 37.5^{\circ}$ C (99.5°F) on axillary setting.
- Gastroenteritis within 72 hours preceding the study vaccine administration.

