9.11 Duration of Follow Up for AE Resolution

Participants will be monitored throughout the study period for adverse events. AEs come to the attention of site clinicians through interim medical histories, physical examinations and laboratory testing conducted to investigate other illnesses or routine tests. The possible occurrence of any AE and SAE will also be asked during the scheduled study visits. In addition, the parents will be advised to contact study staff immediately at any time throughout the study period if their child experiences an AE. All adverse events will be closely monitored in the safety monitoring processes.

AEs will be managed in accordance with good medical practices by the clinical study site team who will assess and treat or refer the participant for medical care as appropriate. Where feasible and medically appropriate, the parent will be encouraged to seek medical care at the facility where the study clinician is based, and to request that the clinician be contacted upon their arrival. If needed to monitor or treat an adverse event, additional study visits may be conducted.

All AEs and SAEs will be followed until resolution, until the condition stabilizes, or until the participant's participation in the study ends, whichever is earlier. Once resolved or stabilized, the appropriate AE / SAE form(s) will be updated. Participants who have an ongoing study product-related AE/SAE at study completion or at discontinuation from the study will be followed by the PI or his designee until the event is resolved or determined to be irreversible, chronic, or stable by the PI. The Investigator will ensure that follow-up includes any supplemental investigations as

Confidential

may be indicated to elucidate the nature and / or causality of the AE or SAE. This may include additional laboratory tests or investigations, histopathological examinations or consultation with other health care professionals.

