- That the child's participation is voluntary and refusal to participate will not result in any fine, loss of rights, or access to medical care that the participant is normally entitled receive.
- In the event of unforeseen circumstances or needs, the investigator may decide to withdraw the participant from continued participation in the research, even without the consent of the parent/LAR.
- That the participant's parent/LAR will be provided with the results of any new important findings related to the trial or the study vaccine which may influence the participant's parent/LARs decision whether or not to continue participation in the research.
- The number of other participants participating in the research.
- Who to notify as the point of contact with the investigator and IRBs in case the parent/LAR would like to know more information regarding the trial and his/her rights as research participants parent/LAR.
- That the investigator is responsible for collecting signed and dated written informed consent forms from the participant's parent/LAR regarding participation in the study before participation is allowed; that he/she will be given a signed and dated copy of the form to keep; and that the investigator must keep an original signed and dated copy of individual's signed and dated written informed consent form in the investigator's research files.

They will be encouraged to ask questions about the study, have the questions answered and then be given time to decide if s/he would like to have her/his child participate in the study. It will be emphasized that participation is voluntary, and that the parent/LAR has the right to decline to participate or subsequently withdraw from the study at any time without prejudice. Parent/LAR will be made aware that authorized representatives of health agencies and POLYVAC and its designee, PATH will have access to their confidential medical information for the purposes of monitoring trial conduct or performing audits.

If the parent/LAR agree to participate in the study they will be asked to sign the consent form. Original ICFs must be kept on file by the investigator for possible inspection by regulatory authorities or POLYVAC. The parent/LAR must receive a copy (or second original) of the signed and dated ICF(s), and any subsequent updates or amendments to the ICF. The study monitor shall check the documentation of the individual ICFs during each monitoring visit.

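### After an investigator-initiated withdrawal, no section requires new SAEs or intussusception to be sought to four weeks after the last dose, yet the infant stays in the safety denominator

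*Protocol*

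**What the plan says.** Protocol Section 7.4 distinguishes stopping vaccination from leaving the study only where the parent declines: that infant may stay for safety assessment. It then lists reasons for withdrawal from the study. Two of these are decided for the individual infant and do not depend on withdrawn consent: "If the Principal Investigator (PI) decides that withdrawal is in the best interest of the participant" and "Significant non-compliance with treatment regimen or trial requirements". Section 15.7 tells parents that "the investigator may decide to withdraw the participant from continued participation in the research, even without the consent of the parent/LAR".

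On what follows, Section 7.4 says: "In the event of withdrawal from study, reasonable efforts should be made to conduct the following procedures". The list is a diary review, an update of ongoing AEs and SAEs, a query about AEs, SAEs and medications since the last visit, a physical examination and updated contact details. All of these look back from the exit.

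Section 9.11 follows AEs and SAEs to resolution, to stabilisation or "until the participant's participation in the study ends, whichever is earlier". It makes one exception: "Participants who have an ongoing study product-related AE/SAE at study completion or at discontinuation from the study will be followed by the PI" or a designee until the event is settled.

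Section 4 promises active surveillance for "SAEs including intussusception over the period between first vaccination and four weeks after the last vaccination will be conducted for all infants". Section 3.2.2 makes the same window a secondary safety endpoint.

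**The concern.** The plan has a safety endpoint with a fixed window and a route out of the study that can close observation before the window does. The route is open to the investigator while consent still stands, so the missing follow-up is avoidable.

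Such loss need not be random. The plan itself expects some withdrawals to be caused by adverse events: Protocol Section 12.4.3 and SAP Table 41 report unsolicited AEs leading to withdrawal from the study, and SAP Listing 1 shows an adverse event as a possible reason for early termination. If observation ends because of an infant's condition, a later event in that infant goes unseen and the SAE and intussusception proportions are too low. With rare events, a single case matters.

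**Working it through.** **Which infants keep follow-up and which do not**

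| Situation | Text | Follow-up after vaccination stops or the infant leaves |
|---|---|---|
| Absolute contraindication after dose 1 | 5.1.3: "the participant must not receive additional doses of the vaccine but should be appropriately followed up for safety by the Investigator" | Yes |
| Known SAE | 9.9: followed to satisfactory resolution, or until chronic or stable; no limit by relatedness | Yes |
| Ongoing product-related AE or SAE | 9.11 exception | Yes |
| Ongoing SAE judged unrelated | 9.9 continues; 9.11 stops when participation ends | Contradictory |
| Temporary contraindication at dose 2, infant withdrawn at the investigator's discretion | 5.1.3 | None stated |
| New event after investigator-initiated withdrawal | 7.4 exit query only | None stated |

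**When endpoint time is lost.** The window closes 28 days after the last dose received. An infant withdrawn at Visit 2 before dose 2 had dose 1 at least 56 days earlier, so the window closed at least 56 − 28 = 28 days before. No endpoint time is lost there, which also covers the temporary-contraindication row. Time is lost only when withdrawal falls within 28 days of a dose: roughly Days 1 to 29, or the 28 days after dose 2.

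**How the analysis treats the infant.** Protocol Section 12.3.4 puts every vaccinated infant with any safety data in the safety population. Section 12.4.5 analyses data collected before withdrawal. Section 12.3.4 allows denominators to vary with available data, but the SAP shells for unsolicited AEs and SAEs (Tables 29 and 35, on which Tables 43 to 51 are modelled) divide by the whole safety population. SAP Section 7.4 treats missing data as missing completely at random, without imputation. An event after withdrawal but inside the window is therefore scored as no event.

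**The plan's nearest safety figure.** Protocol Section 12.2 gives 95% power to see at least one solicited reaction among 550 infants at a true incidence of 0.55%:

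1 − (1 − 0.0055)^550 = 0.952. This reproduces.

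If all of the assumed 10% dropouts were unobserved, n = 550 × 0.9 = 495 and 1 − (1 − 0.0055)^495 = 0.935. That treats loss as unrelated to risk. The point here is possible selective loss, whose size the documents do not give, and it does not rest on this figure.

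**Scale of one unseen event.** Clopper-Pearson two-sided 95% upper limits for the liquid ROTAVIN group:

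- 0/550: 0.67%
- 1/550: 1.01%

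This shows sensitivity to one missed SAE. It does not estimate how often one would be missed.

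**The case against.** The strongest reply is that the infants of most concern are already protected. Section 5.1.3 keeps safety follow-up after hypersensitivity, intussusception and the other absolute contraindications. Section 9.9 follows known SAEs, and Section 9.11 follows ongoing related events. Section 7.4 has an exit query, requires a withdrawn infant with a threatening reaction to be treated or transferred, and has the sponsor told of every premature termination within 48 hours. Parents are told to report later AEs needing care. This stands. A reader might infer that follow-up stops for the infants most likely to have had a problem, or that safety oversight is removed; the documents do not support either reading. None of these provisions, however, has the study look for a new event after exit. Parental reporting is passive and is not tied to the endpoint window.

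Second, Section 4 can be read as describing only infants still in the study. That is possible, but Section 3.2.2 defines the endpoint without that limit, and the denominators keep the withdrawn infant.

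Third, the SAP already separates the two kinds of discontinuation: Table 1 has a block for each, Tables 41 and 42 split AEs the same way, and Listing 1 prints the date of last contact. This also stands. What is missing is a count of infants whose follow-up ended before the window closed.

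Fourth, one might apply an assumed investigator-initiated share to the 10% dropout to count affected infants. The 10% is an all-cause planning figure, and the documents give no split by reason or timing. No such count is supported.

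**Conclusion.** The point holds in a limited form. The protocol lets the investigator take a vaccinated infant out of the whole study while consent stands, and nothing then requires SAE or intussusception status to be obtained to four weeks after the last dose received. The analysis counts an unseen event in that time as no event. Separately, Sections 9.9 and 9.11 contradict each other on ongoing SAEs judged unrelated.

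The gap is confined to investigator-initiated withdrawals within 28 days of a dose and to those unrelated ongoing SAEs. The number of infants is unknown, and Section 7.4 expects withdrawal to be low. Any bias would be towards too few events if withdrawal is linked to the infant's condition. The documents make that possible but give no frequency, so a stated size of bias would not be supported. The change is worth making because it protects a named safety endpoint at little cost.

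**What to change.** Reconcile Protocol Sections 4, 5.1.3, 7.4, 9.9, 9.11 and 15.7 so that, unless consent is withdrawn, the infant is lost or dies, or the study ends, SAE and intussusception status is still obtained, for example by telephone, through four weeks after the last dose received. Extend Section 12.4.5 so that this information enters the safety analysis. Sections 9.9 and 9.11 should state one rule for ongoing SAEs judged unrelated.

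In the SAP, report by vaccine group and reason the infants whose safety follow-up ended before that date, using the existing early-termination and vaccine-discontinuation blocks of Table 1.

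The cost is wording in the protocol, SAP and consent information, plus a few extra contacts. This concerns outcome follow-up and reporting only; no rule on when vaccination should stop is proposed.
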